### 13.6.3 *Tumor Genomic Profile correlative science endpoints:*

All analyses of Oncopanel in correlation with patient outcomes are exploratory and hypothesis-generating. Any promising findings will be explored in future studies.

## 13.7 **Reporting and Exclusions**

### 13.7.1 Evaluation of Efficacy

For this Phase II trial, the efficacy evaluable population is a modified intent-to-treat (ITT) population. The modified ITT population consists of all randomized patients who initiate protocol therapy, even if there are major protocol therapy deviations.

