## 4. REGISTRATION PROCEDURES

### 4.1 General Guidelines for DF/HCC Institutions

Institutions will register eligible participants in the Clinical Trials Management System (CTMS) OnCore. Registrations must occur prior to the initiation of protocol therapy. Any participant not registered to the protocol before protocol therapy begins will be considered ineligible and registration will be denied.

Participants who are randomized, but do not initiate study treatment will be replaced.

The following registration/randomization procedures should be followed:

- An investigator will confirm eligibility criteria and a member of the study team will complete the protocol-specific eligibility checklist.
- The eligibility checklist(s) and all pages of the consent form(s) will be faxed to the ODQ at [contact].
- The ODQ Registrar will (a) review the eligibility checklist, (b) register the participant on the protocol, and (c) randomize the participant.
- An email confirmation of the registration and/or randomization will be sent to the Overall PI, study coordinator(s) from the Lead Site
- Prior to beginning crossover therapy, the crossover eligibility section of the checklist should be completed and signed by the treating investigator and re-faxed to the ODQ at [contact]. The ODQ registrar will review the eligibility checklist, change the subject's treatment arm, and notify the study team.

Following registration, participants may begin protocol therapy. Issues that would cause treatment delays should be discussed with the Overall Principal Investigator (PI). If a participant does not receive protocol therapy following registration, the participant's registration on the study must be canceled. Registration cancellations must be made in OnCore as soon as possible.

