### 4.2 Registration Process for DF/HCC Institutions

DF/HCC Standard Operating Procedure for Human Subject Research Titled *Subject Protocol Registration* (SOP #: REGIST-101) must be followed.

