## **5.8 Duration of Follow Up**

Participants removed from protocol therapy for unacceptable adverse event(s) will be followed until resolution or stabilization of the adverse event.

In patients who come off trial for a reason other than progressive disease, if possible during the follow-up period, scans should be performed every 9 weeks (if the patients is within 27 weeks of

initiation of study treatment) or every 12 weeks (if the patient is greater than 54 weeks from initiation of study treatment) to evaluate for disease progression.

All participants will be followed annually by phone or by medical record until death.

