### 11.1.1 Definitions

**Evaluable for Target Disease response.** Only those participants who have measurable disease present at baseline, have received at least one cycle of therapy, and have had their disease re-evaluated will be considered evaluable for target disease response. These participants will have their response classified according to the definitions stated below. (Note: Participants who exhibit objective disease progression prior to the end of cycle 1 will also be considered evaluable.)

**Evaluable Non-Target Disease Response.** Participants who have lesions present at baseline that are evaluable but do not meet the definitions of measurable disease, have received at least one cycle of therapy, and have had their disease re-evaluated will be considered evaluable for non-target disease. The response assessment is based on the presence, absence, or unequivocal progression of the lesions.

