### **13.4 Analysis of Primary Endpoints**

The primary analysis of the study will be the comparison of PFS per RECIST 1.1 between Arm A and Arm B using logrank test and group sequential methods to control the overall one-sided Type I error rate at 0.1.

The null and alternative hypotheses are defined using the hazard ratio (HR) of the Arm A to Arm B as:

$$\begin{aligned} H_0: & \text{ HR} \leq 1 \\ H_1: & \text{ HR} > 1 \end{aligned}$$

All inferences will be conducted in the intent-to-treat manner, and the survival function will be summarized using the Kaplan-Meier methods according to randomized treatment assignment. Final analysis will be performed after 70 PFS events are observed or at least 12 months after the last patient is enrolled on study, whichever occurs first.

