### **13.5 Analysis of Secondary Endpoints**

#### Efficacy Endpoints

All patients who initiated protocol therapy will be evaluated for PFS per irRECIST criteria, ORR, CBR, and OS. ORR and CBR will be evaluated using RECIST 1.1 and irRECIST criteria (as defined in Section 11.3). DOR will be evaluated among patients who had CR or PR. All these endpoints will be estimated separately in the two treatment arms.

The objective response rate (CR + PR) and immune-related response rate (irCR + irPR) will be reported by arm with 90% exact confidence intervals. Objective response rate and immune-related response rate will be compared between Arm A and Arm B, respectively using a Pearson

chi-squared test for difference in proportions with a one-sided  $\alpha$  of 0.1.

Clinical benefit is defined as CR, PR or SD  $\geq$  27 weeks. Clinical benefit will be calculated using RECIST 1.1 and irRECIST criteria, respectively. Clinical benefit rate (CR+PR+SD $\geq$ 27 wks) per RECIST 1.1 and irRECIST criteria will be reported respectively with 95% exact confidence intervals. CBR will be compared between two treatment arms using a Pearson chi-squared test for difference in proportions with a one-sided  $\alpha$  of 0.1.

PFS per irRECIST and OS will be also analyzed using Kaplan-Meier product-limit estimates and 95% confidence bands. PFS per irRECIST is defined as the time from study randomization to disease progression per irRECIST or death due to any cause, whichever occurred first. Patients alive without disease progression per irRECIST are censored at the date of last disease evaluation. OS is defined as the time from study randomization to death due to any cause. Patients will be censored at the date they were last known alive. The hazard ratio for each time-to-event endpoint will be estimated with 95% confidence intervals derived from the Cox proportional hazard model, but no hypothesis testing will be conducted.

DOOR is defined as the time from CR or PR achieved until renewed disease progression is detected. DOOR will be calculated per RECIST 1.1 and irRECIST criteria, respectively, and descriptive statistics will be used to summarize the intervals observed by arm.

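### Primary PFS has two analysis populations: section 13.4 says intent-to-treat, section 13.7.1 limits efficacy to patients who start therapy, and section 4.1 replaces and cancels never-starters

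*Combined protocol and SAP*

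**What the plan says.** Section 13.4, on the primary PFS comparison: "All inferences will be conducted in the intent-to-treat manner", with patients grouped by the arm drawn at randomization. PFS is timed from randomization (1.2, 13.1).

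Section 13.7.1 calls the trial's efficacy population modified ITT and defines it: "The modified ITT population consists of all randomized patients who initiate protocol therapy, even if there are major protocol therapy deviations". It names no endpoint and makes no exception for primary PFS.

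Section 13.5, for the secondary endpoints: "All patients who initiated protocol therapy will be evaluated for PFS per irRECIST criteria, ORR, CBR, and OS".

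Section 4.1: "Participants who are randomized, but do not initiate study treatment will be replaced". The same section adds: "If a participant does not receive protocol therapy following registration, the participant's registration on the study must be canceled". Section 4.2 defers to a registration SOP (REGIST-101) that is not among the documents.

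Section 5.8 covers survival: "All participants will be followed annually by phone or by medical record until death". For progression, three places bear on a patient who was never treated:
- Study calendar note f ties on-study scans to treatment cycles.
- Section 5.8 asks for scans, if possible, in patients who leave the trial without progression, in windows counted from the start of treatment.
- Calendar note i continues scans every 9 to 12 weeks from the last assessment in patients who went off study without progression. Section 5.9 does not list failure to start treatment among its off-study reasons.

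**The concern.** A patient who is randomized and never dosed belongs in the primary analysis under 13.4 and is left out under 13.7.1. Nothing says which rule prevails, so the choice could be made once results are known, in a trial without blinding.

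Allocation comes before the first dose, so whether a patient starts can depend on the arm assigned. Arm B's option of pembrolizumab at progression weakens the incentive to decline eribulin alone, but does not remove it. If non-starting depends on both arm and prognosis, a treated-only comparison is no longer the one that randomization protects, and the bias can go either way. If 13.4 is the intended rule, replacement and cancellation under 4.1 leave it unclear whether PFS data would exist for these patients.

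**Working it through.** **1. The plan's own figures.** Inputs from 13.2: 70 events, medians 4.1 and 7.1 months, HR 0.58, one-sided alpha 0.1 (critical Z 1.2816).

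Power = Φ(|ln HR| × √(70/4) − 1.2816). At HR 0.58: 0.5447 × 4.1833 = 2.279; 2.279 − 1.282 = 0.997; Φ = 84.1%. At HR 4.1/7.1 = 0.5775 it is 84.5%. Including the futility look (35 events, stop if Z < 0) gives 82.6% and 83.0%. Expected events at month 24 are 69.9. The stated 83% and 70 events reproduce, so the sample size is not in question.

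**2. The two analysis sets.** Let k be the number of never-starters (no rate is given).
- Replaced: 13.4 gives 88 + k patients, 13.7.1 gives 88. With k = 4: 92 against 88.
- Not replaced: 88 against 88 − k. With k = 4: 88 against 84.

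The sets coincide only when k = 0.

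**3. Type I error under no effect (illustrative).** Assumptions, none from the documents: 25% of patients have good prognosis (median PFS 8.0 months) and 75% poor (3.4 months). The overall median is then 4.1, since 0.25 × 2^(−4.1/8.0) + 0.75 × 2^(−4.1/3.4) = 0.175 + 0.325 = 0.50. There are 44 treated patients analysed per arm, with never-starters replaced and excluded. Accrual is uniform over 18 months, dropout 5% per year, with a log-rank test at 70 events and no futility look.

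| Who fails to start | k = 2 | k = 4 |
|---|---|---|
| Arm B, good prognosis twice as likely | 0.105 | 0.110 |
| Arm B, good prognosis three times as likely | 0.108 | 0.115 |
| Arm B, all good prognosis (extreme) | 0.126 | 0.152 |
| Arm B, unrelated to prognosis | 0.101 | 0.103 |
| Arm B, all poor prognosis | 0.097 | 0.089 |
| Arm A, good prognosis twice as likely | 0.099 | 0.094 |
| Arm A, good prognosis three times as likely | 0.095 | 0.089 |

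With no never-starters the figure is 0.102; with them split equally between arms it is 0.101 to 0.103. Simulation error is about 0.0006 for the no-exclusion case and the first two rows, and about 0.001 elsewhere. Keeping all randomized patients, with scans, gives 0.100 to 0.102 in the good-prognosis cases.

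**4. What intent-to-treat costs in power.** Medians are 4.1 against 7.1 months, never-starters are split equally between arms, and those in Arm A progress at the control rate. Latest analysis is month 18 + 12 = 30, from the time limit in 13.4.

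| Never-starters | Power, scanned, not replaced | Power, scanned, replacements added |
|---|---|---|
| 0 | about 84% | – |
| 4 | 81.2% | 81.3% |
| 10 | 76.9% | 77.8% |

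A hand check without replacement shrinks the log hazard ratio by the treated fraction of Arm A. For 4: 0.549 × 42/44 = 0.524; Φ(0.524 × 4.183 − 1.282) = 82%. For 10: 0.549 × 39/44 = 0.487; Φ(0.487 × 4.183 − 1.282) = 77%.

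If never-starters give no PFS data and are not replaced, power stays at 83 to 84% but the analysis comes later. Mean analysis time moves from about month 23.9 to about 25.7 with 4. With 10, about 57% of simulated trials reach month 30 before 70 events, with a mean of about 68 events.

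**The case against.** Two readings would remove the conflict. First, 13.4 could be the specific rule for primary PFS, with 13.7.1 covering the other endpoints. Second, 13.4 could govern only how patients are grouped, with 13.7.1 governing who is included; 4.1 and 13.5 fit that plan. Both are reasonable and neither is stated. They also give opposite answers on never-starters, so clarification is still needed. It is fair to add that a treated-only set is a recognized phase II choice, and that one sentence would settle which population is primary.

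Three stronger readings are tempting and should not be drawn.

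- **Cancellation destroys the progression data.** The meaning of cancellation for data collection rests on the SOP, which cannot be seen here. Section 5.8 may still capture deaths. Note i counts from the last assessment, which could be the baseline scan, so no treatment start date is needed. The documents show that follow-up is unclear, not that it is absent.
- **The ORR comparison has three denominators.** Section 13.5 sets the ORR and CBR population explicitly as patients who started therapy, which matches 13.7.1. It departs from 13.4 only if the reference there to all inferences is carried beyond the primary endpoint. Section 11.1.1 requires that patients "have received at least one cycle of therapy, and have had their disease re-evaluated will be considered evaluable for target disease response", but this says when a response can be classified and is not stated as an analysis denominator.
- **The error rate is materially inflated.** That needs a non-starter rate and a prognostic tilt that the documents do not give.

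**Conclusion.** The conflict in wording is certain: 13.4 and 13.7.1 define different primary PFS sets as soon as one randomized patient is not treated, and 4.1 does not clearly secure the follow-up that 13.4 would need. It should be fixed before any results are seen.

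The size is conditional and probably small. There is no material effect if nobody fails to start, or if non-starting is balanced or unrelated to prognosis. Under the assumed two- to threefold tilt with 2 to 4 Arm B never-starters, error is about 0.5 to 1.5 points above the nominal 0.10 (0.3 to 1.3 above the simulated 0.102). About 0.15 is an extreme case, and a tilt in Arm A makes the test conservative. A reader should not conclude that the trial's type I error is uncontrolled.

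**What to change.** - **13.7.1:** state that primary PFS, and the between-arm OS comparison, use all randomized patients by assigned arm, as 13.4 already promises, with the treated (modified ITT) set as a sensitivity analysis. Align the OS wording in 13.5.
- **4.1:** state that randomized never-starters stay in the study database and in the analysis, and that any replacement is additional. Unless they withdraw consent for data, follow them for survival as in 5.8 and for progression where possible at note i's existing 9 to 12 week interval, counted from the last assessment, which may be the baseline scan.
- **Reporting:** give the number of never-starters and the reasons, by arm.
- **11.1.1:** a note that its evaluability rule does not define the ORR or CBR denominator is enough.

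The cost is a few paragraphs, a few scans, possibly a change in how the registration SOP is applied, and some dilution: power of about 81% with 4 scanned never-starters and 77 to 78% with 10, against about 84%. Where never-starters give no PFS data and are not replaced, the cost is time instead, and with 10 of them the month-30 limit would often come before 70 events. Patients who withdraw consent for data contribute nothing after that date. If the sponsor prefers the treated set as primary, 13.4 must stop describing the analysis as intent-to-treat, and never-starters should still be reported by arm.

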### 13.7.2 Evaluation of Safety

The safety population will be used in the safety data summaries. The safety population consists of all patients who took at least one dose of any randomized treatment and who have at least one post-baseline safety assessment. Note that a patient who had no adverse events constitutes a safety assessment. Patients who have received at least one dose of study drug but have no post-treatment safety data of any kind would be excluded.

## 14. PUBLICATION PLAN

The results should be made public within 24 months of reaching the end of the study. The end of the study is the time point at which the last data items are to be reported, or after the outcome data are sufficiently mature for analysis, as defined in the section on Sample Size, Accrual Rate and Study Duration. If a report is planned to be published in a peer-reviewed journal, then that initial release may be an abstract that meets the requirements of the International Committee of Medical Journal Editors. A full report of the outcomes should be made public no later than three (3) years after the end of the study.

**APPENDIX A**

**PERFORMANCE STATUS CRITERIA**

ECOG Performance Status Scale		Karnofsky Performance Scale	
Grade	Descriptions	Percent	Description
0	Normal activity. Fully active, able to carry on all pre-disease performance without restriction.	100	Normal, no complaints, no evidence of disease.
		90	Able to carry on normal activity; minor signs or symptoms of disease.
1	Symptoms, but ambulatory. Restricted in physically strenuous activity, but ambulatory and able to carry out work of a light or sedentary nature (e.g., light housework, office work).	80	Normal activity with effort; some signs or symptoms of disease.
		70	Cares for self, unable to carry on normal activity or to do active work.
2	In bed <50% of the time. Ambulatory and capable of all self-care, but unable to carry out any work activities. Up and about more than 50% of waking hours.	60	Requires occasional assistance, but is able to care for most of his/her needs.
		50	Requires considerable assistance and frequent medical care.
3	In bed >50% of the time. Capable of only limited self-care, confined to bed or chair more than 50% of waking hours.	40	Disabled, requires special care and assistance.
		30	Severely disabled, hospitalization indicated. Death not imminent.
4	100% bedridden. Completely disabled. Cannot carry on any self-care. Totally confined to bed or chair.	20	Very sick, hospitalization indicated. Death not imminent.
		10	Moribund, fatal processes progressing rapidly.
5	Dead.	0	Dead.

## APPENDIX B

## STRONG CYP3A INDUCERS/INHIBITORS

The list provided below is not exhaustive. For a more comprehensive, frequently updated list, please visit: <http://medicine.iupui.edu/clinpharm/ddis/table.aspx>.

### Medications that strongly inhibit CYP3A:

Amprenavir  
Atazanavir  
Boceprevir  
Clarithromycin  
Conivaptan  
Delavirdine  
Diltiazem  
Erythromycin  
Fosamprenavir  
Indinavir  
Itraconazole  
Ketoconazole  
Lopinavir  
Mibepradil  
Miconazole  
Nefazodone  
Nelfinavir  
Posaconazole  
Ritonavir  
Saquinavir  
Telaprevir  
Telithromycin  
Verapamil  
Voriconazole  
Grapefruit, grapefruit juice, or any product containing grapefruit

### Medications that strongly induce CYP3A:

Carbamazepine  
Felbamate  
Nevirapine  
Phenobarbital  
Phenytoin  
Primidone  
Rifabutin  
Rifampin  
Rifapentine  
St. John's wort

## APPENDIX C

## GUIDELINES FOR COLLECTING RESEARCH BIOPSY TISSUE

Tissue specimens will be collected from metastatic lesions using standard institutional procedures. The amount of tissue collected may follow the guidelines listed below:

*Skin/*chest wall: A goal of 2 4-mm punch biopsies will be obtained.

*Lymph node:* A goal of 5-7 core biopsy specimens will be obtained using an 18-gauge needle.

*Liver:* A goal of 5-7 core biopsy specimens will be obtained using an 18-gauge needle.

*Lung:* Because of the risk of pneumothorax associated with core needle biopsies of lung nodules, no core biopsies of lung nodules are mandated on this protocol, unless they are clinically indicated.

*Bone:* Because the yield of malignant tissue from bone biopsies tends to be relatively low, if a patient has another accessible site of disease (i.e. skin, lymph node, liver), that site should be biopsied preferentially. If bone is the only biopsy-accessible site, then a goal of 3-6 core biopsy specimens will be obtained using an 11-13 gauge needle.

**Please note that the above are guidelines for the amount of tissue to be obtained, and are not meant to replace clinical judgment at the time the procedure is performed.** Less than the goal quantity of tissue is accepted for each type of biopsy, and will be left to the clinical judgment of the physician performing the procedure.

**If a patient is undergoing resection of a lesion for clinical reasons** (i.e. wedge resection of a new lung lesion for confirmation of diagnosis or re-testing of hormone receptor or HER2 status; or, resection of a chest wall lesion; or, resection of a lymph node), then the patient may opt to have a portion of that tissue (roughly equivalent to the goal amount of tissue listed in the guidelines above, i.e. the equivalent of two 5-mm punch biopsies of the skin, or 3-6 18-gauge core biopsies) stored for research at the time of the procedure (provided that the tissue is processed as specified), in which case, the patient would not be required to undergo a separate research biopsy at baseline on this protocol.

Coded laboratory specimens will be stored in the Tumor Bank of the DFCI. These specimens will become the property of DFCI. Patients will be informed that their specimens may be used for research by investigators at DF/HCC and other approved collaborators. Shared specimens will be identified with a sample ID number; all patient identifying material will be removed.

### Risks of Research Biopsy and Procedures for Minimizing Risk

#### Potential risks according to site are:

*Skin/*chest wall (punch biopsy):

- Likely: local discomfort and minor bleeding
- Less likely: moderate or major bleeding, or infection

*Lymph node, liver, or bone (core needle biopsy):*

- Likely: local discomfort and minor bleeding
- Less likely: moderate or major bleeding, need for blood transfusion, hospitalization due to bleeding or other complications, infection, damage to adjacent organs. Additional risks may be present if intravenous conscious sedation is required

*Breast (core biopsy):*

- Likely: local discomfort and minor bleeding.
- Less likely: moderate or major bleeding, need for blood transfusion, hospitalization due to bleeding or other complications, infection, pneumothorax, damage to adjacent organs.

*Pleural fluid (thoracentesis):*

- Likely: local discomfort and minor bleeding
- Less likely: moderate or major bleeding, need for blood transfusion, hospitalization due to bleeding or other complications, infection, pneumothorax, damage to adjacent organs

*Ascites fluid (paracentesis):*

- Likely: local discomfort and minor bleeding
- Less likely: moderate or major bleeding, need for blood transfusion, hospitalization due to bleeding or other complications, infection, bowel perforation or damage to adjacent organs. In order to minimize the risk of a biopsy, only qualified personnel will perform these procedures.

Prior to the procedure, the physician performing the procedure will discuss the risks with each study participant, answer any questions, and obtain separate procedure consent. Patients will be evaluated for comorbidities or concomitant medications that may increase the risk of potential complications. For biopsies of lesions that are not superficial and clearly palpable, imaging studies such as CT or ultrasound will be used to guide the biopsy in order to minimize the risk of damage to adjacent structures. After lymph node biopsies, patients will be observed a minimum of 2 hours (range 2-4 hours) after the procedure, or according to standard institutional guidelines. After liver biopsies, patients will be observed a minimum of 4 hours (range 4-6 hours) after the procedure, or according to standard institutional guidelines. Less than the goal quantity of tissue is accepted for each type of biopsy, and will be left to the clinical judgment of the physician performing the procedure.

